## 7.2 Sample size

The primary endpoint of this study is an AUC of the ROC curve analysis on CRI values to predict altered peripheral perfusion determined with the CRT test. Sample size for subjects with altered peripheral perfusion required to obtain desired AUC is calculated with the following equation [9]:

$$n = \frac{Z_{\alpha/2}^2 \times V(AUC)}{d^2}$$

where,  $Z$  is the standard normal deviate determined with probability of type I error:  $\alpha$ ,  $d$  is the desired width of one-half of the confidence interval (CI), and  $V(AUC)$  is variance of AUC which is derived from the following equation [10]:

$$V(AUC) = (0.0099 \times e^{-a^2/2}) \times \{(5a^2 + 8) + (a^2 + 8)/\kappa\}$$

where,  $a = \varphi^{-1}(AUC) \times 1.414$ ;  $\varphi^{-1}$  is inverse of standard cumulative normal distribution; and  $\kappa$  is the ratio of the number of subjects without the altered peripheral perfusion to the number of subjects with the altered peripheral perfusion. Based upon our preliminary data:

- The prevalence of the subjects with altered peripheral perfusion is expected to be 30%, and then  $\kappa$  is 2.33.
- We hypothesize that the AUC will be 0.84, and then  $a = \varphi^{-1}(0.84) \times 1.414 = 1.406$ .

Therefore,  $V(AUC)$  can be calculated as follow:

$$V(AUC) = (0.0099 \times e^{-1.406^2/2}) \times \{(5 \times 1.406^2 + 8) + (1.406^2 + 8)/2.33\} = 0.0816$$

To achieve an AUC of at least 0.70 which is considered as fair [11], one-half of the CI:  $d$  should be 0.14 with the hypothesized AUC of 0.84. At the significance level of 5% (probability of type I error:  $\alpha = 0.05$ ), the number of subjects with altered peripheral perfusion is derived as:

$$n = \frac{Z_{\alpha/2}^2 \times V(AUC)}{d^2} = \frac{1.96^2 \times 0.0816}{0.14^2} = 15.99 \approx 16$$

The total number of required sample size given by  $n(1 + \kappa)$  is 54. Considering possible early withdrawals of subjects, we plan to recruit up to 60 subjects to achieve 54 evaluable subjects (10% of drop-out rate).

## 7.3 The level of significance and the power of the clinical investigation

All statistical tests will be assessed at the significance level of 5% (probability of type I error:  $\alpha = 0.05$ ).

#### 7.4 Expected drop-out rates

Although the drop-out rate for this study is unknown, relatively high drop-out rate can be expected since the study site is the ED and the subjects may need early withdrawals due to disposition (admission to the hospital or discharge). Therefore, we use 10% of drop-out rate and will recruit up to 60 subjects to achieve 54 evaluable subjects.

#### 7.5 Pass/fail criteria to be applied to the results of the clinical investigation

The hypothesis to be tested in this study is that CRI is capable to detect subjects with altered peripheral perfusion determined with the CRT test, as described in the section 5.2. A criterion to accept the hypothesis is that the AUC value described in the section 6.1.3 (1) "Primary endpoint" is at least 0.70 which is considered as fair [11].

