#### 5.3 Claims and intended performance of the investigational device that are to be verified

##### (1) Capillary Refill Index (CRI)

- Display range: 0.1 ~ 99.9 seconds

\*CRI will not be claimed as an intended for use in a regulatory application for FDA clearance of OLV-4201A Pulse Oximeter. CRI will be included in the regulatory application as an index intended for clinical research only, not for diagnosis.

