#### 6.1.3 Primary and secondary endpoints

##### (1) Primary endpoint

The primary endpoint is the area under the curve (AUC) of the receiver operator characteristic (ROC) curve analysis on CRI values to predict the altered peripheral perfusion determined with the CRT test. A specific cutoff value for CRI has not yet been determined, then the AUC value will be used to summarize comprehensive capability of CRI to detect the altered peripheral perfusion. Procedures of the measurement of CRI and CRT, and statistical methods are described in the section 6.4 "Procedures" and the section 7 "Statistical considerations", respectively.

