## 6.1.6 Any procedures for the replacement of subjects

No replacement condition is foreseen. Subjects who withdraws early will not be replaced as we plan to recruit up to 60 subjects to achieve at least 54 subjects to be analyzed as described in the section 7.2 "Sample size".

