## 7 Statistical considerations

### 7.1 Statistical design, method and analytical procedures

In order to assess the study aims and hypotheses, we will describe the study sample using descriptive statistics such as frequencies, proportions, means, standard deviations, 95% confidence intervals, medians, and interquartile ranges. The mean of the three repeated CRI and CRT measurements will be considered as the values for each subject.

The primary and secondary endpoints are described in the section 6.1.3. Receiver operator characteristic (ROC) curve analysis will be performed and area under the curve (AUC) will be calculated to demonstrate capability of CRI to predict altered peripheral perfusion determined with the CRT test. An optimal cutoff value for CRI will be determined with the ROC analysis and the sensitivity and the specificity in differentiating altered peripheral perfusion will be calculated. Pearson's, or Spearman's correlation coefficient will be calculated to assess the correlation between CRI and CRT values.

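### Section 7.2 sizes the study for 0.70 as a lower 95% limit, but 7.5 passes on the AUC estimate alone, so a pass does not establish an AUC of at least 0.70

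*Combined protocol and SAP*

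**What the plan says.** The primary endpoint in 6.1.3 is the AUC for CRI against altered perfusion as judged by the visual CRT test; "the AUC value will be used to summarize comprehensive capability of CRI to detect the altered peripheral perfusion". Section 7.1 says that "Receiver operator characteristic (ROC) curve analysis will be performed and area under the curve (AUC) will be calculated to demonstrate capability of CRI". It lists 95% confidence intervals among the statistics describing the sample, but names no interval method for the AUC.

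The number 0.70 appears in two roles.

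- **Section 7.2 (sample size).** "To achieve an AUC of at least 0.70 which is considered as fair [11], one-half of the CI" is set to 0.14 around a hypothesised AUC of 0.84. Here 0.70 is the lower end of a two-sided 95% interval.
- **Section 7.5 (pass/fail).** "A criterion to accept the hypothesis is that the AUC value described in the section 6.1.3 (1) 'Primary endpoint' is at least 0.70". Here 0.70 is a threshold for the estimate, with no interval or test attached.

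Section 7.3 adds: "All statistical tests will be assessed at the significance level of 5" per cent. It gives no null value for the AUC and no power. The hypothesis in 5.2 is qualitative: that CRI can detect altered perfusion.

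The 16 altered subjects in 7.2 follow from an expectation, "The prevalence of the subjects with altered peripheral perfusion is expected to be 30" per cent. What the plan fixes is the total: "we plan to recruit up to 60 subjects to achieve at least 54 subjects to be analyzed" (6.1.6). No minimum number of altered subjects is set.

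**The concern.** A study sized so that the interval around 0.84 just reaches 0.70 would be expected to judge success by that interval. Section 7.5 judges it by the estimate, and an estimate of exactly 0.70 is as likely to lie above the true AUC as below it. Sections 7.2 and 7.5 read together let a pass be reported as showing at least fair discrimination, when the rule gives no such assurance.

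At stake is the wording of the primary conclusion. Section 17 says the results will be used in applications for FDA clearance of the device, so the pass statement should claim only what the rule supports.

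A secondary question is whether a pass near 0.70 still excludes 0.50 if fewer altered subjects are enrolled than expected.

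**Working it through.** **1. The plan's own figure.** Inputs from 7.2: AUC 0.84, a = 1.406, κ = 2.33, d = 0.14, z = 1.96.

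V = 0.0099 × exp(−a²/2) × {(5a² + 8) + (a² + 8)/κ} = 0.0817 (plan: 0.0816).

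n = 1.96² × 0.0817 / 0.14² ≈ 16.0 (plan: 15.99, taken as 16).

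Total = 16 × 3.33 = 53.3, taken as 54; 54/0.9 = 60. The arithmetic reproduces.

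**2. How often the 7.5 rule passes at 16 + 38.** SE = √(V/16) from the same formula with κ = 38/16 = 2.375, and P(pass) = 1 − Φ((0.70 − AUC)/SE). The last column is from simulation: equal-variance binormal data, empirical AUC, at least 20,000 trials per setting.

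| True AUC | SE | P(pass), formula | P(pass), simulation |
|---|---|---|---|
| 0.50 | 0.0839 | 0.9% | 1.0% |
| 0.60 | 0.0837 | 12% | 12% |
| 0.65 | 0.0832 | 27% | 28% |
| 0.70 | 0.0821 | 50% | 51 to 52% |
| 0.84 | 0.0713 | 98% | 98% |

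**3. What an observed 0.70 supports at 16 + 38.** Symmetric (Wald): 0.70 ± 1.96 × 0.0821 = 0.54 to 0.86. On the logit scale, with SE 0.0821/(0.70 × 0.30): 0.52 to 0.83. Both exclude 0.50, and both extend well below 0.70.

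**4. Dependence on the number altered, out of 54 evaluable.** Limits are for an observed 0.70 with the 7.2 variance. False acceptance at AUC 0.50 uses the rank-sum null SE = √(55/(12 × n₁ × n₀)).

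| Altered | Lower limit, Wald | Lower limit, logit | False acceptance at 0.50 |
|---|---|---|---|
| 16 | 0.539 | 0.520 | 1.1% |
| 12 | 0.522 | 0.4997 | 1.8% |
| 9 | 0.500 | 0.474 | 3.0% |
| 8 | 0.490 | 0.462 | 3.7% |
| 7 | 0.477 | 0.447 | 4.5% |
| 6 | 0.461 | 0.428 | 5.6% |

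By the plan's symmetric formula, a borderline pass stops excluding 0.50 at about 9 or fewer altered. With a logit interval this happens at about 12 or fewer, and only just at 12. If the number altered is binomial with 54 subjects and 30% prevalence (an assumption), 9 or fewer has a 2% chance and 12 or fewer a 13% chance. These figures matter only when the observed AUC is close to 0.70.

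**The case against.** The strongest reply is that the plan never says a pass proves an AUC of at least 0.70. Section 5.2 claims only that CRI can detect altered perfusion, and 7.5 repeats that hypothesis. Any rule based on an estimate passes about half the time at its own threshold, so the pass rates at 0.65 and 0.70 are errors only against a claim the plan does not state. For the claim it does state, the rule is strict: about 1% false acceptance at the planned mix, and below 5% down to 7 altered of 54. Section 5.3 also bounds the consequence: "CRI will be included in the regulatory application as an index intended for clinical research only, not for diagnosis".

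All of this stands, and it rules out three stronger readings.

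- *The plan claims an AUC of at least 0.70 on a pass.* A reader might infer this from the wording in 7.2, but neither 5.2 nor 7.5 says it.
- *The pass rule fails to control error, or contradicts the hypothesis.* It does neither at the planned case mix.
- *The sample size is wrong.* The 7.2 calculation is sound for the precision target it sets.

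The case-mix worry is also easily overstated. It needs a marked shortfall in altered subjects together with a borderline AUC, and the figure of 12 rests on choosing a logit interval.

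What the reply does not remove is that one number has two meanings in 7.2 and 7.5, no section reconciles them, and no interval for the AUC is tied to the conclusion.

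**Conclusion.** The point holds and is minor. The sample size in 7.2 corresponds to a lower-limit criterion, while 7.5 uses a point-estimate criterion at the same value. At 16 + 38 a pass is good evidence of discrimination better than chance. It is not evidence that the AUC is at least 0.70: a true AUC of 0.65 passes about 28% of the time, and an estimate of 0.70 is compatible with values from about 0.54 to 0.86.

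Loss of the exclusion of 0.50 at low numbers of altered subjects is secondary (about a 2% chance of 9 or fewer at 30% prevalence, under the symmetric formula).

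The figures rest on the 7.2 variance formula, a binormal model for the simulated rates, and a binomial number of altered subjects. The documents give no prevalence other than the expected 30%.

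**What to change.** At the same sample size:

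1. **Section 7.5.** Keep the 0.70 threshold for the estimate. Report the AUC with a two-sided 95% interval by one pre-specified method (for example DeLong variance with Wald or logit limits). State that acceptance supports discrimination better than chance when the lower limit exceeds 0.50, and supports an AUC of at least 0.70 only when the lower limit is itself at least 0.70.
2. **Section 7.2.** Replace the phrase about achieving an AUC of at least 0.70 with a statement that an estimated AUC of 0.84 would have a lower 95% limit of about 0.70 (symmetric interval, half-width 0.14).
3. **Optional, 7.5.** Make a lower limit above 0.50 a formal second pass condition, as a safeguard against few altered subjects. At 16 altered it changes almost nothing: the pass rate at a true AUC of 0.84 stays at about 98%. The downside comes with fewer altered subjects. At 8 altered the pass rate falls from about 95% to 93 to 94% (Wald) or 88% (logit).

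Items 1 and 2 cost a few sentences and no subjects.

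Passing only when the lower limit is at least 0.70 would be a different, stricter claim and is not proposed. At 16 + 38 and a true AUC of 0.84 it would succeed about half the time by the planning formula (about 46% with logit and 63% with Wald limits in simulation). For 80% power it would need (1.96 + 0.84)² × 0.0817/0.14² ≈ 32.7, so 33 altered and 33 × 3.33 ≈ 110 evaluable subjects.

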#### 7.6 Provision for an interim analysis

No interim analysis is planned.

#### 7.7 Criteria for the termination of the clinical investigation on statistical grounds

As no interim statistical analysis is planned, no criteria for the termination of the study is defined.

#### 7.8 Procedures for reporting any deviation(s) from the original statistical plan

Any modification to the statistical analysis plan will be documented in the final study report if applicable.

#### 7.9 Specification of subgroups for analysis

Not applicable.

#### 7.10 Procedures that take into account all the data

Not applicable. This study is the observational study and no allocation of subjects is planned.

#### 7.11 Treatment of missing, unused or spurious data, including drop-outs and withdrawals

- Data collected up to the point of the subject's withdrawal will continue to be used and analyzed.
- If just one value of CRI/CRT out of the three repeated measurements is missing, the mean of the remaining two values will be used as the value for the subject.

#### 7.12 Exclusion of particular information from the testing of the hypothesis

- Data of a subject in which two or more values of CRI/CRT out of the three repeated measurements are missing will be excluded from the analysis.

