### 6.2.2 Justification of the choice of comparator(s)

The comparator is the visual CRT, which is typically used to assess peripheral blood perfusion at the bedside. The CRI measurement has been developed to assess peripheral blood perfusion quantitatively as an alternative method to the visual CRT test. Therefore, comparisons between CRI and CRT need to be performed.

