#### **CRI measurement by the investigational device**

The  $SpO_2$  sensor probe will be applied to either the index or middle fingertip of the same hand of the subject used in the CRT measurement, depending upon which fingertip was compressed in the CRT measurement. For example, if the index fingertip was used in the CRT measurement, then the sensor will be applied to the middle fingertip. With the sensor on it, the investigator will compress the subject's fingertip for five seconds by the investigator's finger as same way of the traditional CRT test. The sensor is flexible and thus, the investigator is able to compress the fingertip by compressing the sensor (Figure 2). The compression will be performed with signals from the device, and then the device will measure CRI.

**Figure 2:** Compression for the CRI measurement

The investigator will confirm the sensor probe is properly applied to the fingertip by measuring CRI and checking whether the shape of the CRI measurement waveform is proper. With proper application of the sensor probe, the measurement waveform is convex upward as shown in Figure 3. If the sensor probe is not properly applied, the investigator will replace the sensor probe.

**Figure 3:** Proper shape of the CRI measurement waveform

The investigator will be blinded from the measured value of the CRI measurement.

All subjects are free to withdraw from the study at any time and for any reason. The investigators will immediately discontinue any procedures and remove any research instruments from the subject. Data collected until the subject's point of withdrawal from the study will be analyzed. The estimated duration of the subject's participation is approximately 15 minutes in total.

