#### (2) Case Report Form (CRF)

The CRFs are the primary data collection instruments for the study. All data requested on the CRFs must be recorded. All missing data must be explained. If a space on the CRF is left blank because the procedure was not done, or the question was not asked, write "N/D". If the item is not applicable to the individual case, write "N/A". All entries should be printed legibly in ink. If any entry error has been made, to correct such an error, draw a single straight line through the incorrect entry and enter the correct data above it. All such changes must be initialed and dated. **DO NOT ERASE OR WHITE OUT ERRORS.** For clarification of illegible or uncertain entries, print the clarification above the item, then initial and date it.

The PI is responsible for ensuring the data and information are properly recorded on each subject's CRF and related documents. The PI and an investigator who completes the recording will sign the CRF to validate that the data and the information are recorded on the CRF correctly and completely.

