#### (4) Data review

The PI will continuously review the aggregate data to ensuring integrity of the study data. The PI is

responsible for identifying missing data and exclusion of data described in the section 7.11 and 7.12.

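### Section 7.12 does not separate CRI non-results from early departures: report the exclusions by cause and add one sensitivity AUC

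*Combined protocol and SAP*

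**What the plan says.** Each subject has three CRI and three CRT measurements, taken alternately, and the means are analysed (sections 6.1.2 and 7.1). If one of three is missing, section 7.11 says "the mean of the remaining two values will be used as the value for the subject". Beyond that, section 7.12 applies: "Data of a subject in which two or more values of CRI/CRT out of the three repeated measurements are missing will be excluded". Neither section makes the rule depend on why a value is missing.

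The hypothesis is accepted if the AUC "is at least 0.70 which is considered as fair" (section 7.5). The only source of loss that the plan discusses is departure from the ED: "relatively high drop-out rate can be expected since the study site is the ED and the subjects may need early withdrawals due to disposition" (section 7.4).

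Section 8.1 (2) requires that "All missing data must be explained" on the CRF, and section 8.1 (4) makes the PI "responsible for identifying missing data and exclusion of data described in the section 7.11 and 7.12". At the bedside, section 6.4.1 provides: "If the sensor probe is not properly applied, the investigator will replace the sensor probe". It does not say what happens if no usable CRI is obtained even so.

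Section 7.1 plans general descriptive statistics, one ROC analysis with its AUC, a cutoff with sensitivity and specificity, and a correlation. Section 7.10, on taking all the data into account, is marked not applicable.

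**The concern.** The two kinds of missing CRI mean different things. A subject who leaves for admission or discharge tells us nothing about the device. A subject with a valid CRT, whose fingertip was compressed for CRI but who got no usable value, tells us something about how CRI performs. That matters for a method described in section 6.2.2 in these terms: "The CRI measurement has been developed to assess peripheral blood perfusion quantitatively as an alternative method to the visual CRT test".

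Under section 7.12 both subjects drop out of the AUC without distinction. If CRI non-results were more common in altered (or in unaltered) perfusion, the planned output would not show it. With only about 18 altered subjects expected among 60, a few such exclusions are enough that a reader should be able to see them. At stake is how the AUC is interpreted, not whether it is computed correctly.

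**Working it through.** **The plan's own figures (section 7.2).** With AUC 0.84 and κ = 2.33, the variance formula gives V(AUC) = 0.0817 (stated 0.0816). Then n = 1.96² × 0.0816 / 0.14² = 15.99, taken as 16 altered subjects; 16 × 3.33 = 53.3, rounded up to 54; 54 / 0.9 = 60. These reproduce apart from rounding. The proposed change does not alter the sample size.

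**Inputs for the illustration.**
- 60 recruited and 30% altered (section 7.2): A = 18 altered, U = 42 unaltered, T = 18 × 42 = 756 pairs.
- AUC 0.84 among subjects with a CRI value (the section 7.2 hypothesis).
- Assumed: valid CRT in all 60, with f altered and g unaltered CRI non-results. The documents give no value for f or g.

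**Formulas.** Let m = (18 − f)(42 − g), the pairs in which both members have a CRI value.
- Ties: (0.84m + 0.5(T − m)) / T
- Least favourable limit: 0.84m / T
- Most favourable limit: (0.84m + (T − m)) / T

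| f, g | m | Least favourable | Ties | Most favourable |
|---|---|---|---|---|
| 2, 0 | 672 | 0.747 | 0.802 | 0.858 |
| 3, 0 | 630 | 0.700 | 0.783 | 0.867 |
| 4, 0 | 588 | 0.653 | 0.764 | 0.876 |
| 1, 1 | 697 | 0.774 | 0.813 | 0.852 |
| 2, 2 | 640 | 0.711 | 0.788 | 0.865 |
| 2, 4 | 608 | 0.676 | 0.773 | 0.871 |

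For example, f = g = 1: 0.84 × 697 = 585.48 and T − m = 59. So 585.48/756 = 0.774, (585.48 + 29.5)/756 = 0.813 and (585.48 + 59)/756 = 0.852.

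**When does tie scoring cross 0.70?** The tie formula equals 0.5 + 0.34m/T, which is below 0.70 only if m < 0.20 × 756 / 0.34 = 444.7. With failures among altered subjects only, f = 7 gives m = 462 and 0.708, and f = 8 gives m = 420 and 0.689. Mixing the groups does not get there with fewer failures: f = 7, g = 1 gives m = 451, still above 444.7. Section 7.4 allows for 6 losses in all; even if all 6 were altered CRI non-results, m = 504 and the tie-scored AUC is 0.727.

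**Why the limits use opposite ends.** For f = 2, g = 4, ranking all six non-results lowest gives (510.72 + 64 + 4)/756 = 0.766, and ranking all six highest gives (510.72 + 76 + 4)/756 = 0.781. The true limits are 0.676 and 0.871, so ranking everyone at the same end does not bound the result.

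**Why the number of CRI values alone cannot define the added subjects.** Measurements alternate. A subject who leaves after CRT, CRI, CRT has two CRT values and one good CRI value. Section 7.12 excludes that subject for missing CRI, yet the device worked. The cause has to enter the definition.

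**The case against.** The strongest reply is that the problem may never arise. No section reports a CRI failure; section 3.2 mentions none in the 30-subject preliminary study, although silence is not evidence of none. When the device withholds a value is left to Attachment 5, which is not among the documents reviewed. Probe replacement and the two-value rule also make such exclusions less likely. All of this stands, and it limits the weight of the point.

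Much of the information would also be collected. Besides the CRF explanations, the PI tracks premature sensor removal (section 4.6), early withdrawals are documented with reasons (section 16.3), and protocol deviations are discussed before analysis (section 10.2). That is correct, but none of it feeds a planned table or analysis, and a non-result under correct procedure is not a deviation.

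Section 5.3 says CRI will not be claimed as an intended use and is for clinical research only. This supports leaving the primary question as discrimination among measured values. It does not remove the interest in seeing how often CRI gave no value.

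A non-result is visible to the user, so scoring it 0.5 mixes feasibility with discrimination. That is a fair reason to keep such an AUC supplementary and to put the table first.

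A reader might infer that section 7.12 inflates the AUC, or that 0.676 shows the pass criterion to be in danger. The documents support neither. The direction of bias is unknown. The 0.676 figure is a mathematical limit that ranks failures by their true status and assigns the whole planned 10% loss to the device, whereas section 7.4 attributes losses to disposition.

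**Conclusion.** The point holds as an inexpensive improvement. Section 7.12 is pre-specified and can remain the primary rule; it is not an error. The gap is that its exclusions are not separated by cause, so the AUC compared with 0.70 covers only subjects in whom CRI returned enough values, and the recorded causes go unused.

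The size is unknown because no failure rate is given. Under the stated assumptions (18 altered, 42 unaltered, valid CRT in all, AUC 0.84 where CRI exists), two altered non-results scored as ties move the AUC from 0.84 to 0.802. That shift of 0.038 is well inside the plan's own half-width of 0.14. It takes 8 altered non-results among 18 to bring the tie-scored AUC below 0.70, which is more than the 6 losses planned for all causes together. Only the extreme limits cross 0.70 sooner, at 4 altered failures (0.653) or at 2 altered with 4 unaltered (0.676).

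A reader might also infer that everyone with fewer than two CRI values should be restored. That would count early leavers as device failures and repeat the mixing of causes.

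**What to change.** Keep the section 7.12 complete-case AUC as primary and add to section 7.12:

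1. A table of the subjects excluded under 7.12, by cause: withdrawal or disposition; CRI measured but no value returned or waveform unusable; CRT missing. Split it by CRT status where CRT is valid. Take the cause from the CRF explanations and settle it at the data review, before the analysis.
2. One sensitivity AUC. To the analysed subjects, add only those with a valid CRT whose CRI compressions were performed but gave fewer than two values because the device returned no usable result. Score every pair involving such a subject as a tie (0.5). The opposite-end limits are optional and, if shown, should be labelled as mathematical limits.
3. A statement that subjects whose CRI readings are missing because they left early, and subjects without a valid CRT, stay excluded.

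The cost is a few sentences, one small table and one extra AUC on data the CRF already requires. Bedside procedures and sample size do not change. The downside is a supplementary figure that may be less favourable than the primary AUC. If there are no CRI non-results, the table says so and the AUC is unchanged.
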